### 7.2 Statistical Methods

#### Descriptive Statistics

Statistical analysis will include Student T-test, Chi-square for categorical differences. An interim analysis will be performed when half of subjects are enrolled.

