### **3.4 Primary Endpoints**

- A. The number of patients with a high-grade glioma who achieve a > 50% reduction in focal seizures with PER 4 mg daily after failing 1 or more ASDs at 3 and 6 months.
  1. The overall survival of patients with high-grade glioma treated with PER at 3 months.
  2. Decline in neuropsychological function at 6 months.

All comparisons will use intent to treat model for patients initiated or exiting PER therapy. In event of patients not surviving till 12 months, most recent data prior to death will be used for correlation.

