## 4 Subject Selection Enrollment and Withdrawal

### 4.1 Inclusion Criteria

1. The subject, or the subject's legally acceptable representative is willing to participate in a clinical trial, provides written informed consent, and subject provides written assent, as required by the Mayo Clinic Institutional Review Board (IRB) policy involving human subjects. In the event of subject lacking the capacity or losing the ability to consent, consent will be deferred to subject's legally acceptable representative
2. Subjects that meet the following diagnostic criteria:
  - a. Patients with established clinical diagnoses of biopsy-proven high-grade glioma (Grade II or above) and epilepsy refractory to at least 1, drug with a seizure frequency of at least 1 seizure episode per 3-months prior to baseline visit.
3. Subjects with body weight of  $\geq 40$  kg and  $\leq 125$  kg at screening.
4. Adults age 18 and older.

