#### **4.3 Subject Recruitment, Enrollment and Screening**

Subjects (n = 20), will be male and female adults with a high-grade glioma recruited from Mayo Clinic in Jacksonville, Florida- [name], DO, (PI). 10 subjects will be enrolled into an adjunctive Perampanel and other ASDs group, and 10 subjects will receive only alternative ASDs. There will be a 6-month recruitment period for screening and enrollment. The treating physician will decide, based on best medical practice, which patients are candidates for adjunctive Perampanel and other ASDs, or only alternative ASDs. Patients taking Perampanel will begin their titration phase upon enrollment.

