#### Handling of Missing Data

Study data will be collected and managed using REDCap electronic data capture tools hosted at Mayo Clinic. All data requested on the Case Report Form (CRF) will be recorded for each participant. A standardized CRF will be generated by REDCap. For any data query, the Principal Investigator and Investigators will meet to clarify the data queried and make corrections based on consensus. Once the study is completed, the Principal Investigator will randomly select 3 participants and compare the data documented for each on the CRF with what is entered into the REDCap database. If there is any discrepancy, the Principal Investigator and/or Investigators will cross-reference all 20 patients to ensure accuracy.

**Primary Hypothesis:** We hypothesize that perampanel will lead to a significant reduction in seizure frequency for adult patients with brain tumor-related seizures associated with high-grade glioma.

We will compare seizure frequency before and 3 months after treatment with monotherapy and adjunctive PER and use descriptive statistics to demonstrate differences in responders. A P-value < 0.05 will be used to reflect statistical significance.

**Secondary Hypothesis 1:** We hypothesize the progression of brain tumor (comparing 4 and 8 mg/d of perampanel) based upon fusion by comparing baseline brain MRI and MRI at 12 months will be less for IDH-mutants.

We hypothesize there will be minimal or no change in neurocognitive function from 0 to 3 months on Montreal Outcome Cognitive Assessment (MOCA; higher scores indicating greater function); and the Clinical Global Impression of Change (CGIC; scores from 1 to 7, with lower scores indicating greater improvement and a score of 4 indicating no change).

Chi-square and Student T-test will be used to measure differences in assessment and change during the study period. A P-value < 0.05 will be considered significant.

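### For seizure frequency the plan offers only a t-test, with no outcome scale or baseline covariate; a baseline-adjusted log-rate analysis of the same diaries would be more efficient at no extra cost

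*Combined protocol and SAP*

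**What the plan says.** Section 7.2, Descriptive Statistics, gives the methods: "Statistical analysis will include Student T-test, Chi-square for categorical differences". Further on in 7.2, the primary-hypothesis paragraph says "We will compare seizure frequency before and 3 months after treatment with monotherapy and adjunctive PER", describes responders with descriptive statistics, and adds "A P-value < 0.05 will be used to reflect statistical significance". The secondary-hypothesis text, after MOCA and CGIC, says "Chi-square and Student T-test will be used to measure differences in assessment and change during the study period". Nowhere is there a transformation, a count or rate model, or a baseline covariate.

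The endpoint in Section 3.4 is binary: "The number of patients with a high-grade glioma who achieve a > 50% reduction in focal seizures". On group size, Section 4.3 says "10 subjects will be enrolled into an adjunctive Perampanel and other ASDs group, and 10 subjects will receive only alternative ASDs", and on assignment "The treating physician will decide, based on best medical practice, which patients are candidates for adjunctive Perampanel". Section 4.1 admits patients "with a seizure frequency of at least 1 seizure episode per 3-months prior to baseline visit" and sets no upper limit. Section 3.1 gives a different floor: one seizure per month over a 2-month retrospective baseline. Section 7.1 calls the study a pilot that is not powered for effectiveness.

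**The concern.** Seizure frequency with a low floor and no ceiling usually has a long right tail. With 10 patients per arm, one or two high-frequency patients can dominate both the mean and the SD on the untransformed scale. Using baseline by subtraction does not cure this, because absolute change is largest in the same patients. Percent change is unstable at low baselines: a patient going from 1 seizure to 3 scores +200%, while the best possible score is −100%.

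A log-rate analysis with log baseline as covariate pulls in the tail and removes the between-patient variation that baseline predicts. What is at stake is the precision of the one seizure-frequency comparison the pilot will produce. That comparison is to be tested at P < 0.05, is likely to feed the interim efficacy look in 7.2, and should inform the decision on a larger trial.

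**Working it through.** **Nothing to reproduce.** The sample size of 20 is a feasibility target. The documents give no effect size, SD, correlation or power.

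**Inputs from the documents.** 10 per arm (4.3); threshold 0.05 (7.2), taken as two-sided; comparison at 3 months (7.2); a 2-month seizure calendar before treatment, then monthly (3.5); entry floor of 1 per 3 months (4.1) or 1 per month (3.1).

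**Assumed inputs.** Seizure-rate distribution, baseline-to-follow-up correlation, effect size, no dropout, and arms comparable apart from treatment. All comparisons below are between arms.

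**1. Baseline adjustment alone, on the log scale (normal approximation).**

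Power = Φ( |ln RR| / (SD·√(2/n)) − 1.96 ). With adjustment, SD becomes SD·√(1 − r²).

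Take n = 10, log-SD 1.0 and RR 0.5. Then |ln 0.5| = 0.693, √(2/10) = 0.447, and 0.693/0.447 = 1.550.

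- Unadjusted: Φ(1.550 − 1.96) = 34%
- r = 0.5: 1.550/0.866 = 1.790, power 43%
- r = 0.7: 1.550/0.714 = 2.170, power 58%
- r = 0.9: 1.550/0.436 = 3.556, power about 95%

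**2. Simulation with log-normal patient rates.** Poisson counts, 2-month baseline with at least 1 seizure, 3-month follow-up, 4,000 trials per scenario. Medians were 1, 4 or 10 seizures per month, between-patient log-SD 0.5, 1.0 or 1.5, and within-patient log-SD 0.3 or 0.7, making 18 scenarios. ANCOVA used log((count + 0.5)/months). Power at a true 50% reduction in four of them:

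| Median / between SD / within SD | t, follow-up | t, change | t, percent change | log ANCOVA |
|---|---|---|---|---|
| 1 / 0.5 / 0.3 (low skew) | 37% | 24% | 28% | 38% |
| 4 / 1.0 / 0.7 | 12% | 11% | 14% | 27% |
| 4 / 1.0 / 0.3 | 18% | 32% | 45% | 56% |
| 10 / 1.5 / 0.3 (high skew) | 7% | 23% | 58% | 68% |

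Over all 18 scenarios at a 50% reduction, ANCOVA power runs from 23% to 83%. The share of that power kept by each t-test is:

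- follow-up frequency: 10–98%, median about 43%
- change: 24–66%, median about 46%
- percent change: 41–86%, median about 65%

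With no effect, ANCOVA rejects in 4.5–5.8% of trials and the t-test on follow-up in 1.9–4.6%. The gain is not bought with type I error.

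**3. Simulation with gamma patient rates.** Shape 0.5 or 1, mean 1–8 per month, extra within-period gamma variation of shape 3, 2- or 3-month baseline, true reduction 50–60%. Power is about 11–28% for a t-test on follow-up or change, 15–30% on percent change, and 20–49% for log ANCOVA, with type I error about 5% for ANCOVA.

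**4. Two limits on the ANCOVA.** At a mean of 1 seizure per month many patients have no follow-up seizures, and the added constant pulls the exponentiated coefficient towards 1: for a true ratio of 0.40 the median estimate was 0.49–0.51. The period also matters. At that mean, using a single month of follow-up cuts ANCOVA power to 20–23%, against 12–19% for the follow-up t-test.

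**The case against.** Several stronger readings are tempting, and the documents do not support them.

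- **That the plan ignores baseline.** It does not. Section 7.2 plans a before-and-after comparison, and the responder endpoint in 3.4 is relative to the patient's own baseline. What is missing is the form of the comparison.
- **That the plan runs a t-test on raw counts.** This is inferred from silence. The explicit t-test sentence follows MOCA and CGIC, and the primary paragraph names no test. The narrower statement is safe: a t-test is the only method offered for a numeric outcome, and no scale is given.
- **That half the power is lost.** Half is a mid-range result for follow-up frequency and change under assumed skew. No figure can be derived from the documents, and percent change, the scale closest to the responder definition, loses less.

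The best remaining defence is that this is a non-randomised pilot which disclaims power, so confounding limits the result more than test efficiency does. The point about confounding stands: the simulations assume comparable arms, and physician choice does not guarantee them. The disclaimer does not settle the matter, because 7.2 still tests at P < 0.05 and a pilot needs a precise estimate more than it needs a P-value. A fair technical objection also stands: log(rate + constant) does not estimate a rate ratio when rates are low. The fix allows for that.

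**Conclusion.** The point holds as a free improvement. On any of the three t-test readings (follow-up, change, percent change), log-rate ANCOVA had higher power in every scenario with a true effect. Under moderate to high skew and a 50–60% reduction the contrast is about 11–28% or 15–30% against 20–49%. At low skew the follow-up t-test loses almost nothing (37% against 38%); at high skew it keeps about a tenth (7% against 68%). These sizes rest entirely on assumed rate distributions and effects, with no dropout and comparable arms. Even the better analysis has modest power in many settings, so it does not turn the pilot into a test of effectiveness, and it does not remove confounding.

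**What to change.** 1. Reconcile the baseline definitions in 3.1 (one per month over 2 months) and 4.1 (one per 3 months, or about 0.33 per month) first. The floors differ threefold, and the baseline rate cannot be defined until they agree.
2. Keep the responder endpoint of Section 3.4.
3. For the seizure-frequency comparison in 7.2, replace the t-test with ANCOVA of log seizure rate over the whole 3-month follow-up diary, not month 3 alone, on treatment group and log baseline rate. Fix the constant in advance, for example 0.5 seizure added to each count.
4. Report the rate ratio with 95% CI from a negative binomial model with log baseline rate as covariate and log follow-up time as offset. With 20 patients its large-sample interval is approximate, so take the P-value from the ANCOVA. Alternatively, report the ANCOVA ratio and label it as a ratio of (rate + constant).
5. Give rank ANCOVA or the Wilcoxon test as a sensitivity analysis.
6. State that arms are assigned by the treating physician, so adjustment for baseline rate addresses that one measured imbalance and no other confounding.

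The cost is wording in Section 7.2 and the reconciliation in item 1. The seizure diaries already supply the data; no visit, patient or assessment is added.

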#### Handling of Missing Data

Study data will be collected and managed using REDCap electronic data capture tools hosted at Mayo Clinic. All data requested on the Case Report Form (CRF) will be recorded for each participant. A standardized CRF will be generated by REDCap. For any data query, the Principal Investigator and Investigators will meet to clarify the data queried and make corrections based on consensus. Once the study is completed, the Principal Investigator will randomly select 3 participants and compare the data documented for each on the CRF with what is entered into the REDCap database. If there is any discrepancy, the Principal Investigator and/or Investigators will cross-reference all 20 patients to ensure accuracy.

**Primary Hypothesis:** We hypothesize that perampanel will lead to a significant reduction in seizure frequency for adult patients with brain tumor-related seizures associated with high-grade glioma.

We will compare seizure frequency before and 3 months after treatment with monotherapy and adjunctive PER and use descriptive statistics to demonstrate differences in responders. A P-value < 0.05 will be used to reflect statistical significance.

**Secondary Hypothesis 1:** We hypothesize the progression of brain tumor (comparing 4 and 8 mg/d of perampanel) based upon fusion by comparing baseline brain MRI and MRI at 12 months will be less for IDH-mutants.

We hypothesize there will be minimal or no change in neurocognitive function from 0 to 3 months on Montreal Outcome Cognitive Assessment (MOCA; higher scores indicating greater function); and the Clinical Global Impression of Change (CGIC; scores from 1 to 7, with lower scores indicating greater improvement and a score of 4 indicating no change).

Chi-square and Student T-test will be used to measure differences in assessment and change during the study period. A P-value < 0.05 will be considered significant.

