Study Product, Dose, Route, Regimen	PER is a noncompetitive AMPA glutamate receptor antagonist. The two phases of the treatment portion of this study include a titration phase and a stable dosing phase. This study will have two treatment arms consisting of PER and alternative ASD arm. The PER arm will begin a titration phase with 2mg PER PO q.d. (may be split to b.i.d.) for one week and increase by 2mg/week until reaching an initial dose of 4mg PO q.d. (q.d. or b.i.d. dosing) is reached. Flexible dosing of PER above 4mg to a maximum of 8 mg daily will be compared to use of alternative ASDs and be guided by best clinical practices with dosing and indication within U.S. FDA guidelines.
Duration of Administration	Participants will be assigned to receive open label PER or an alternate ASD for at least 12 week and up to 40weeks for the remainder of the study. This includes 2-4 weeks of titration and up to 40 weeks of stable dosing. Reduction by 2 mg will be allowed in cases of efficacy if doses greater than 4 mg daily result in non-idiopathic side-effects.
Reference therapy	All comparisons will use standard ASDs as the reference therapy using an intent to treat study design for patients initiating or tapering off PER therapy.
Statistical Methodology	Statistical analysis will include Student T-test, Chi-square for categorical differences. An interim analysis will be performed when half of the targeted subjects are enrolled.

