## 2 Study Objectives

### Primary Objective

Demonstrate the efficacy and safety of PER on seizure frequency in adult patients with biopsy-proven high-grade glioma and focal Epilepsy compared with alternate ASDs.

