### 5.3 Method for Assigning Subjects to Treatment Groups

Participants will be assigned to receive:

Group A: open label arm of adjunctive PER (study drug) for patients with seizures treated with at least 1 ASD administered in escalating divided doses of 2 mg/week to 4 mg daily with flexible dosing to 8 mg/day by 4 weeks. Subjects must undergo forced titration of 2 mg/week and be able to tolerate 4 mg to continue in the study. Concomitant ASD will be utilized according to best clinical practice.

or

Group B: continued open label treatment for patients with seizures treated with at least 1 ASD, as per best medical practice, without the use of PER.

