### 5.6 Prior and Concomitant Therapy

Concomitant therapy will allow 0-3 concomitant ASDs. No specific drugs will be disallowed; concomitant ASDs and non-ASDs (e.g. narcotics, benzodiazepines, and barbiturates) will serve as exclusionary therapies when deemed clinically relevant according to best clinical practice.

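### The primary objective compares PER with alternate ASDs, but section 7.2 and the primary endpoint never turn this into a specified Group A versus Group B analysis of seizure frequency

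*Combined protocol and SAP*

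**What the plan says.** The objective is comparative. Section 2 states it as: "Demonstrate the efficacy and safety of PER on seizure frequency in adult patients with biopsy-proven high-grade glioma and focal Epilepsy compared with alternate ASDs". The Study Summary adds, under Reference therapy: "All comparisons will use standard ASDs as the reference therapy". Section 4.3 enrols 10 patients on adjunctive PER and 10 without it, with the treating physician choosing the group.

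The analysis text is different.

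- **Primary hypothesis (section 7.2).** It predicts a significant fall in seizure frequency with PER and names no comparator.
- **Primary analysis (same place).** "We will compare seizure frequency before and 3 months after treatment with monotherapy and adjunctive PER". The sentence goes on to "use descriptive statistics to demonstrate differences in responders", without naming the groups, and significance is set at P < 0.05.
- **Tests (section 7.2, Descriptive Statistics).** "Statistical analysis will include Student T-test, Chi-square for categorical differences". They are not described as paired or two-sample and are not attached to an endpoint.
- **Primary endpoint A (section 3.4).** It counts patients "who achieve a > 50% reduction in focal seizures with PER 4 mg daily" at 3 and 6 months. There is no matching count for Group B.

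**The concern.** A before-after comparison in treated patients measures everything that changed over the period. Section 3.1 puts all patients on radiotherapy plus temozolomide, and section 1.1 says that antitumour therapies help seizure control. Section 5.3 lets concomitant ASDs vary with best practice. Improvement common to both arms is therefore plausible on the protocol's own account, and only Group B can show it.

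If section 7.2 is followed literally, a nominally significant fall, or a PER-only responder count, could be presented as the answer to the comparative objective even if Group B changed by the same amount. Two analysts could also follow the section and report different primary results. Section 7.1 calls the study an unpowered pilot, so its useful product is a between-arm estimate with its uncertainty. The plan does not ask for one.

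**Working it through.** **1. Plan's own figure.** The sample size is 20, and 10 + 10 = 20 agrees with section 4.3. Section 7.1 gives no effect size, variance or response rate, so there is nothing further to reproduce.

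**2. What is specified for a Group A versus Group B contrast in seizure frequency.**

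| Element | Stated? |
|---|---|
| Outcome and reference | Yes: section 2 and Study Summary |
| Group contrast in the analysis text | No: before versus after, group label ambiguous |
| Summary measure and estimate | No |
| Test tied to the contrast | No |
| Responder count in Group B | No: endpoint A is PER only |

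**3. Illustration: inputs.** All are assumptions, because the documents give no seizure-rate data. Patient rates are gamma distributed (shape 0.7 or 1.0, mean 2 or 4 per month). Within-person gamma variation has variance 0.1 or 0.3 in each period, with Poisson counts. This gives 2 × 2 × 2 = 8 scenarios. Follow-up is 3 months, with 10 patients per arm and **no PER effect**. The entry rule is either section 4.1 (at least 1 seizure in 3 months) or section 3.1 (at least 1 per month over 2 months, taken as at least 2 in 2 months). The test is two-sided at 0.05 (sidedness is not stated), so the nominal chance of a result favouring PER is 2.5%. Ranges below are across scenarios, 20,000 trials each.

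**4. Before-after test in Group A.** t = mean(d) / (s_d/√10), where d is follow-up rate minus baseline rate. Chance that it favours PER:

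| Shared fall | Section 4.1 entry | Section 3.1 entry |
|---|---|---|
| 0% | 2-3% | 3-7% |
| 10% | 3-6% | 6-13% |
| 20% | 6-13% | 10-23% |
| 30% | 12-24% | 18-40% |

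The excess at 0% under section 3.1 entry is regression to the mean after selection on a recent count.

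Cross-check: a 30% fall equals 0.29-0.44 SD of the change (section 4.1) or 0.35-0.56 SD (section 3.1). For normal data and n = 10, a shift of 0.3 SD (0.3 × √10 = 0.95) gives P < 0.05 in 14% of trials. A shift of 0.5 SD (0.5 × √10 = 1.58) gives 29%. These agree with the table.

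**5. Between-arm analysis, same data, exchangeable arms.** The t-test on change favours PER in 1.7-2.3% of trials. ANCOVA of log(follow-up rate + 1) on log(baseline rate + 1) and group favours PER in 2.2-2.8% (two-sided rejection 4.6-5.3%). The shared fall cancels.

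**6. Arms that are not exchangeable (ANCOVA).** If Group A fell 30% and Group B 0% for reasons other than PER, the result favours PER in 11-21% of trials. If Group A's baseline rate is 1.5-2 times Group B's, two-sided null rejection is 5-9%, mostly against PER.

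**7. Endpoint A with no change at all.** A reduction of more than 50% occurs in 17-30% of patients (section 4.1 entry) or 19-34% (section 3.1 entry) from count variation alone. That is 10 × 0.17 = 1.7 to 10 × 0.34 = 3.4, so about 2-3 of 10.

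**8. What the between-arm analysis can deliver.** For a true halving by PER, ANCOVA reaches P < 0.05 in about 26-52% of trials on top of a 30% shared fall, and in about 28-57% without one. Responders of 5/10 versus 3/10 give an exact 95% interval of about -24 to +55 percentage points.

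**The case against.** The strongest reply is that the comparison is already in the plan. The Study Summary sets the reference, section 2 names outcome and comparator, and a t-test and chi-square can serve two groups. The phrase about differences in responders may well mean differences between arms. This stands as far as intent goes: a between-arm comparison is clearly meant, and a reader who inferred that the plan had abandoned it would be wrong. What is missing is the contrast in the analysis section, with its summary measure, test and estimate.

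Two other readings are tempting and are not supported.

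- **That Group B has no 'before treatment' date.** Section 5.3 does describe it as "continued open label treatment for patients with seizures treated with at least 1 ASD". But sections 1.5 and 5.2 speak of alternative ASDs being instituted, and sections 3.1 and 4.1 tie the baseline to the screening or baseline visit for everyone. The anchors conflict; they are not absent.
- **That 'monotherapy' means PER alone, so Group B is left out of the sentence.** Section 5.6 gives some room for this: "Concomitant therapy will allow 0-3 concomitant ASDs". However, section 3.1 requires a current regimen of at least one ASD, and sections 4.3 and 5.3 define Group A as adjunctive. A loose label for the two arms is at least as plausible. The phrase is ambiguous, since Group B may take several ASDs, but it does not show that an arm was omitted.

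It may also be said that this is an unpowered pilot. That does not close the gap, because section 7.2 keeps P < 0.05 for the before-after result.

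**Conclusion.** The point holds as a failure to carry the objective through, and it should be corrected. The objective and Study Summary name the comparison; section 7.2 and endpoint A do not specify it, and what they do write cannot separate a PER effect from change shared by both arms.

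The size depends on assumed seizure rates and an assumed shared fall. The protocol supports the direction of such a fall, not its amount. At 30%, the before-after test favours an ineffective PER in about 12-24% or 18-40% of trials, against about 2-3% between exchangeable arms. A reader might infer that the before-after test misleads in any event. It does not: with no shared fall there is essentially no inflation under section 4.1 entry, and only a modest excess (3-7%) under section 3.1 entry.

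Nor does the between-arm contrast give an unbiased answer here. Allocation is by physician choice, so selection bias would remain.

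**What to change.** In section 7.2:

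1. Name as the primary comparison the Group A versus Group B difference in change in seizure frequency from baseline to 3 months, adjusted for baseline frequency, reported as an estimate with a 95% confidence interval.
2. Report responders (more than 50% reduction) in **both** groups at 3 and 6 months, with an exact confidence interval for the difference.
3. Use one baseline window and one index date for both groups, reconciling sections 3.1, 3.5, 4.1 and 5.3. The Day 7 visit in the Schedule of Events is one possible index date.
4. Make the within-PER before-after change descriptive.
5. Label the between-arm comparison exploratory and non-randomised, and state that physician allocation leaves selection bias.

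The model is a matter of choice. If ANCOVA on log(rate + 1) is used, state that the added 1 is its rule for zero counts and that its ratio is on the rate + 1 scale. For example, a fall from 2 to 1 per month reads as (1 + 1)/(2 + 1) = 0.67. In the assumed scenarios a true halving reads as about a 25-38% reduction. State also that its null rejection of about 5% is for exchangeable arms.

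**Cost.** A short amendment for the IRB (section 11). No new visits or data are needed: diary review is scheduled for all subjects, and only drug dispensing and accountability are restricted to the PER arm. The intervals will be wide and nominal significance unlikely, as the working shows. Selection bias is disclosed, not removed.

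The conflict between intent to treat (Study Summary, section 3.4) and the protocol-compliant population (section 7.3), and the strength of the verb that opens the objective, are separate points.
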